### **2.1.8. Analysis Population**

The analysis population for the extension study analysis will be the Safety population. The Safety population will consist of all subjects who receive at least one dose of study drug in this study. If a subject receives dispensed drug but has not returned the blister card (eg, lost follow-up), the subject will be included in the Safety population (ie, treated as taking at least one dose).

### **2.1.9. Analysis Group and Analysis Subgroup**

A total of three analysis groups will be formed based on a subject’s previous participation of double-blind core studies. Column group “301/325/326” that combines these three analysis groups will be also presented. Summary tables will be labeled as follows:

- 301-Lur: Subjects continued from Study D1050301
- 325-Lur: Subjects continued from Study D1050325
- 326-Lur: Subjects continued from Study D1050326
- 301/325/326-Lur: All subjects combined

Subjects continued from Study D1050301 will be further grouped into 3 analysis subgroups (hereafter, referred as ‘Analysis Subgroup A’). Depending on the type of safety analysis in summary table they will be labeled as follows (ie, with 2 additional pooled groups: AllLur-Lur and 301-Lur):

- Pbo-Lur: previously randomized to placebo
- Lur40-Lur: previously randomized to lurasidone 40 mg/day
- Lur80-Lur: previously randomized to lurasidone 80 mg/day
- AllLur-Lur: previously randomized to lurasidone (40 mg/day or 80 mg/day)
- 301-Lur: subjects continued from study D1050301

Subjects continued from Study D1050325 will be further grouped into 3 analysis subgroups (hereafter, referred as ‘Analysis Subgroup B’). Depending on the type of safety analysis in summary table they will be labeled as follows (ie, with 2 additional pooled groups: AllLur-Lur and 325-Lur):

- Pbo-Lur: previously randomized to placebo
- Lur20-Lur: previously randomized to lurasidone 20 mg/day
- Lur60-Lur: previously randomized to lurasidone 60 mg/day
- AllLur-Lur: previously randomized to lurasidone (20 mg/day or 60 mg/day)
- 325-Lur: subjects from study D1050325

Subjects continued from Study D1050326 will be further grouped into 2 analysis subgroups (hereafter, referred as ‘Analysis Subgroup C’). Depending on the type of safety analysis in summary table they will be labeled as follows (ie, with one additional pooled groups: 326-Lur):

- Pbo-Lur: previously randomized to placebo
- Lur-Lur: previously randomized to lurasidone 20-80 mg/day
- 326-Lur: subjects from study D1050326

Subjects may be further grouped into 4 analysis subgroups based on the age at OL baseline (years) as needed (hereafter, referred as ‘Analysis Subgroup D’). Depending on the type of safety analysis in summary table they will be presented as follows (ie, with 2 additional pooled groups: 6-12 years old and  $\geq$  13 years old):

- 6-9 years old
- 10-12 years old
- 6-12 years old (ie, combined group of ‘6-9 years old’, ‘10-12 years old’)
- 13-15 years old
- $\geq$  16 years old
- $\geq$  13 years old (ie, combined group of ‘13-15 years old’, ‘ $\geq$  16 years old’)

To fulfill EMA’s request, for subjects continued from study D1050301, selected safety summary will be also presented by following age subgroup as needed:

- 13 to 14 years old
- $\geq$  15 years old

Summary tables, wherever applicable, will be presented for all subjects in the study by analysis group and by analysis subgroup as needed.

### **2.1.10. Average Dose and Predominant Dose**

The predominant dose (ie, modal dose, used interchangeably hereafter in this document) in the open-label treatment period is defined as the lurasidone dose to which the subject was exposed for the greatest. If a subject has 2 or more doses with the great duration, the one with higher dosage will be selected as predominant treatment.

The average total daily dose during the open-label treatment phase will be calculated as the sum of the total daily dose divided the treatment duration (see [Section 2.2.2.4](#)). The average total daily dose during a visit period is defined in a similar way.

The predominant dose and average total daily dose in the first 52-weeks period are defined in a similar way; specifically, for a subject, the treatment duration in the first 52-weeks period (in days) is defined to be same as the treatment duration in open-label treatment period if the subject was early terminated by Week 52 visit; otherwise, it is defined as the amount of elapsed time between the first day that study medication was taken and the Week 52 visit date (inclusive).

For any study visit, if medication kit usage information is incomplete (ie, meet one of following conditions: any dispensed medication kit at the visit has missing number of tables returned, or

has missing dosing start or ending date), average total daily dose at the visit will not be derived and will be set as missing. For an assessment period that involves multiple study visits (eg, the open-label treatment period), if at some visit(s) the drug usage information is incomplete, then the other visits with complete information of kit usage will be used to derive the average daily dose and predominant dose accordingly.

### **2.1.11. Presenting ‘Endpoint’ in Outputs for Final Analysis**

For safety summary, data will be summarized by visit, Week 52 Endpoint, and ‘Endpoint’ . For effectiveness summary, data will be presented by study visit, ‘Week 52 LOCF’, and ‘Endpoint’.

### **2.1.12. Age over Time**

The following ages will be derived: age (years) at DB Screening, age (years) at OL Baseline, age (years) at Endpoint.

### **2.1.13. Subgroup Analysis**

For a limited number of descriptive analyses, data will be presented for analysis group and analysis subgroup C by subgroup as below as needed:

- Age group at OL Baseline (years): “6-9 years”, “10-12 years”, “6-12 years”, “13-15 years”, “ $\geq$  16 years”, “ $\geq$  13 years”.
- Country: US, Non-US.

For analysis subgroup C, age subgroups to be displayed in output will be “10-12 years”, “13-15 years”, “ $\geq$  16 years”, “ $\geq$  13 years”.

### **2.1.14. Data Imputation Rules**

#### **2.1.14.1. Composite Score**

Imputation rule of each assessment in this extension study will be consistent with what was specified in core studies. That is to say, unless otherwise specified, any individual missing item in any scale will not be imputed. When calculating a total score, subscale score, composite score, or any assessment with more than one item (e.g., CDRS-R total score, ABC subscale scores, CY-BOCS, CGSQ , PANSS total score, PQ-LES-Q, BARS, SAS, AIMS, etc.), if one or more items are missing at a visit, then the associated score (ie, total score or subscale score) will be set to missing. Same as the core studies, the only exceptions are the standardized composite score of the CogState Computerized Cognitive Test Battery, and the category scores of UKU. See

[Section 2.6.9](#) for missing imputation rule of Cogstate standardized composite score and [Section 2.6.11](#) for missing imputation rule of the UKU category scores and UKU total score.

## **Endpoint**

In the event of missing data at Endpoint, the last post-OL baseline observation carried forward approach prior to Endpoint will be used to impute missing values to obtain Endpoint;

## **Week 52 LOCF/Week 52 Endpoint**

In the event of missing data at Week 52 (per visit window in [Section 2.1.3](#)), the last post-OL baseline observation carried forward approach prior to Week 52 will be used to impute missing values.

## **OL Baseline Assessment**

If a value at OL Baseline visit (ie, Week 6 visit in core study) is missing, no imputation will be made.

### **2.1.14.2. Incomplete/Missing Dates**

#### **2.1.14.2.1. Start/End Date for Adverse Event**

Treatment-emergent adverse events (AEs) are those events defined in [Section 2.6.4](#). A conservative approach will be used to handle the missing dates for AE onset date and end date to identify the treatment-emergent AE (ie, if the available incomplete date cannot determine treatment emergent status, the AE will be considered as a treatment-emergent AE). No imputation will be done to calculate AE duration.

#### **2.1.14.2.2. Start/End Date for Prior/Concomitant Medication**

Partial dates of non-study medication start/end date need to be imputed in order to classify the medications as prior or concomitant medications. A conservative approach will be used to handle the incomplete date(s) for medication start/end date (ie, if the available incomplete date(s) cannot determine the concomitant relationship relative to the open-label treatment period, the medication will be considered as a concomitant medication).

#### **2.1.14.2.3. Start/End Date of Psychiatric Hospitalization**

The duration (days) of the hospitalization during the open-label treatment period is calculated as discharge date – hospitalization admission date +1. If the admission date and the discharge date are completely or partially missing, no imputation will be done. If admission date is prior to the start of open-label treatment period, it will be imputed by the start date of open-label treatment period; if discharge date is after the last day of OL treatment phase, it will be imputed by the last day of the OL treatment period. See [Section 2.1.2](#) for definition of start/end of open-label treatment period.

#### **2.1.14.2.4. First Menses Date**

A conservative approach will be used to handle the incomplete date of the first menses date. The partial first menses date will be imputed as follows: (1) If year and month are known, and if the year or month is previous to Screening, use the 15th of the month; otherwise, if the month is the month of Screening, use the 1st of the month. (2) If only year is known, and it is previous to the year of Screening, use June 30th of that year; otherwise, if the year is the year of Screening, use the Jan 01 of the year. No imputation will be done if the first menses date is completely missing.

#### **2.1.14.2.5. Adverse Event Grade and Relationship to Study Medication**

The Adverse Event with missing severity will be classified as ‘unspecified’; similarly, the AE with missing causality to study medications will be classified as ‘unspecified’ as well.

#### **2.1.14.2.6. Lab Data**

Where applicable, the upper limit of quantification (ULOQ) will be substituted for chemistry, hematology, urinalysis, and urine microscopic values that are greater than the ULOQ. Similarly, if the value is below the lower limit of quantification (LLOQ), then the LLOQ will be substituted.

#### **2.1.14.3. BMI**

At each visit, BMI will be derived only when both height and weight are available at the visit and no imputation will be made if one or two of them are missing.

#### **2.1.14.4. Z-score and Percentile of Height, Weight, and BMI per WHO and CDC Growth Reference**

Age-and-sex specific z-scores and percentiles in height and BMI will be derived at each assessed visit using WHO 2007 growth reference for each subject. Considering that no weight related growth reference is available per WHO standard, for each subject (US and non-US), CDC 2000 growth chart for weight will be used to derive age-and-sex specific z-scores and percentiles in weight. In addition, for US subjects, age-and-sex specific z-scores and percentiles in height and BMI will be also derived using CDC 2000 growth chart.

For height and BMI, for summary of z-score and percentile of analysis group or analysis subgroups A and C (ie, studies D1050301 and D1050326), WHO based ones will be reported; for summary of analysis subgroup B (ie, study D1050325) or US only population, the ones per CDC growth chart will be displayed.

For weight, for summary of z-score and percentile of analysis group or analysis subgroup, CDC based ones will be reported consistently.

## **2.2. Methods of Analysis**

### **2.2.1. Statistical Hypotheses for Trial Objectives**

Because of the nature of an open-labeled study, no hypotheses are planned and to be tested.

### **2.2.2. Subject Information**

Unless otherwise specified, subject information will be presented by analysis group and analysis subgroup as needed (see [Section 2.1.9](#)) for the safety population.

#### **2.2.2.1. Demographic and Baseline Characteristics**

Demographic and baseline characteristics will be summarized by analysis group and analysis subgroup for the safety population.

Baseline descriptive statistics (N, mean, SD, median, and range) of demographic characteristics will be provided by analysis group and analysis subgroup for age at OL baseline (in years), body weight, height, body mass index (BMI, calculated as weight(kg)/ [height(m)]), and waist circumference. At OL Baseline, age-and-sex specific z-scores and percentiles in height and BMI will be obtained using WHO 2007 growth reference (see [Attachment 4.1](#)); corresponding z-score and percentile in weight will be obtained using CDC 2000 growth chart. In addition, age-and-sex specific z-scores and percentiles in height weight and BMI at OL Baseline will be reported using CDC 2000 growth chart for US subjects as well.

The number and percentage of subjects in each of the following categories (and sub-categories) at OL baseline will also be summarized by analysis group and by analysis subgroup:

- Gender: Male, Female;
- Race: white, black or African American, Asian, American Indian or Alaska Native, Native Hawaiian or other Pacific Islander, Other;
- Ethnicity: Hispanic or Latino, Not Hispanic or Latino;
- Age at OL Baseline group 1: ≤12 years, 13-17, 18-20 years;
- Age at OL Baseline group 2: ≤9 years, 10-12 years, 13-15 years, 16-17, 18-20 years;
- OL Baseline category for height (WHO): <5th, 5th to <95th, >95th percentile;
- OL Baseline category for weight (CDC): <5th, 5th to <95th, >95th percentile;
- OL Baseline BMI category (WHO): <3th, 3th to 85th, >85th to 97th, >97th percentile;
- Country: US, non-US;
- Region: North America, South America, Europe, and Asia;

The number and percentage of subjects in each of the following categories (and sub-categories) at OL baseline will also be summarized by analysis subgroup for subjects from D1050325 or overall US subjects from D1050301, D1050325, and D1050326 as well:

- OL Baseline category for height (CDC): <5th, 5th to <95th, >95th percentile;
- OL Baseline category for weight (CDC): <5th, 5th to <95th, >95th percentile;
- OL Baseline BMI category (CDC): <5th, 5th to 85th, >85th to 95th, >95th percentile;

Baseline summary statistics (N, mean, SD, median, and range) of disease characteristics will be provided by analysis subgroup for subjects continued from Study D1050301

- DB Baseline and OL Baseline of PANSS total score
- DB Baseline and OL Baseline of CGI-S score

Baseline summary statistics (N, mean, SD, median, and range) of disease characteristics will be provided by analysis subgroup for subjects continued from Study D1050326

- DB Baseline and OL Baseline of CDRS-R total score
- DB Baseline and OL Baseline of CGI-BP-S score

### **2.2.2.2. Disposition Information**

Subject disposition for all enrolled subjects will be summarized by analysis group and analysis subgroup using the following categories:

- Subjects who entered the extension study;
- Subjects who entered the extension study, but not dosed;
- Subjects in the Safety population;
- Subjects in the Safety who completed the study;
- Subjects who discontinued.

Subject disposition for one year study (ie, at Week 52) will be also presented using a similar way for the above categories with one more category for number and percentage of subjects who were still ongoing at 1-year cut.

For subjects who are consented and discontinue from the study, the corresponding reasons for discontinuation will be summarized. Kaplan-Meier plot of the time to early discontinuation will be presented by analysis group.

### **2.2.2.3. Treatment Compliance**

At each post OL-baseline (Weeks 2 – 104) visit, prior to dispensing study medication, previously dispensed study medication will be retrieved and assessed by tablet count.

Compliance in the open-label treatment phase will be calculated for each post-OL baseline visit, the first 52-weeks treatment period, and overall as follows:

- Percent compliance = (number of tablets taken / number of tablets should have taken) x 100.
- Number of tablets taken = number of tablets dispensed – number of tablets returned.
- Number of tablets should have taken = (number of tablets supposed to take in a day) x (number of exposure days).
- Number of exposure days = last dose date – first dose date + 1.

For subjects assigned to the 20 mg per day or 40 mg per day dose, number of tablets supposed to be taken in a day is 1 tablet; for subjects assigned to the 60 mg per day or 80 mg per day, number of tablets supposed to be taken in a day is 2 tablets. If the number of tablets returned is missing, compliance will be set as missing.

For any study visit, if medication kit usage information is incomplete (ie, meet one of following conditions: any dispensed medication kit at the visit has missing number of tables returned, or has missing dosing start or ending date), compliance rate at the visit will not be derived and will be set as missing. For an assessment period that involves multiple study visits (eg, the open-label treatment period), if at some visit(s) the drug usage information is incomplete, then the other visits with complete information of kit usage will be used to derive the compliance rate.

Non-compliance is defined as less than 75% or more than 125% non-missing compliance with the study medication. Subjects with missing compliance are not classified as non-compliant.

Descriptive summary statistics (N, mean, median, and range) will be provided by analysis group and by analysis subgroup, respectively, for percent compliance by study visit. In addition, the number and percentage of subjects in the categories of the following variables will be also summarized by study visit:

- Compliant;
- Non-compliant (<75% or >125%);
- Non-compliant: <75%;
- Non-compliant: >125%;
- Missing.

Incomplete medication kit usage information will be summarized for overall OL treatment period by analysis group as follows: incomplete kit usage for 1 visit period, 2 visit periods, 3 visit periods,  $\geq$  4 visit periods.

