9.2. Treatment Compliance

All subjects and caregivers will be reminded at each study visit of the importance of strict compliance with taking study medication as directed, with food. Compliance with study medication must be monitored closely at each visit. Subjects will be instructed to bring all unused study medication with them to each visit. Subjects missing more than 25% or taking more than 125% of scheduled doses between visits must be immediately reported to and discussed with the Medical Monitor.

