10.7. Study Drug Accountability

Study drug must be received by the investigator or a designated person at the study site, handled and stored safely and properly, and kept in a secured location to which only the investigator and/or designated assistants have access. Study medication is to be dispensed only in accordance with the protocol.

The investigator (or qualified designee) is responsible for maintaining accurate records of the study drug received from the Sponsor, the amount dispensed to and returned by the subjects, and the amount remaining at the conclusion of the study. At the end of the study, all study medication including unused, partially used, and empty blister cards must be returned to the Sponsor, or designee, after confirmation with the CRA. The investigator will be provided with instructions on the return of all study drug. The following information is to be included in the eCRF: visit medication dispensed, blister card number, time of dose, dosing start/stop dates, number of tablets dispensed, blister card return status and number of tablets returned.

If the investigation is terminated, discontinued, suspended, or completed, all unused study drug will be returned to the Sponsor's designee, unless other instructions are provided in writing by CRO/Sponsor.

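### By-visit compliance in SAP 2.2.2.3 is measured only from first to last dose date, so a temporary stop before an attended visit scores 100% for that interval

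*SAP*

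**What the plan says.** SAP 2.2.2.3 sets the level of calculation: "Compliance in the open-label treatment phase will be calculated for each post-OL baseline visit, the first 52-weeks treatment period, and overall as follows". The ratio is "Percent compliance = (number of tablets taken / number of tablets should have taken) x 100", with "Number of tablets taken = number of tablets dispensed – number of tablets returned". The denominator is the daily tablet number (one for 20 or 40 mg, two for 60 or 80 mg) times exposure days, and "Number of exposure days = last dose date – first dose date + 1". Non-compliance is a value below 75% or above 125%, and the classes are tabulated by study visit.

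At visit level the dates appear to be those of the kits. The same section sets the visit's rate to missing if a dispensed kit lacks a dosing start date, a dosing end date or a return count. Protocol 10.7 lists these among the eCRF items: "visit medication dispensed, blister card number, time of dose, dosing start/stop dates". SAP 2.2.2.4 defines treatment duration over the same kind of span, from the first to the last day on which medication was taken.

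Protocol 9.2 uses the same limits on another base: "Subjects missing more than 25% or taking more than 125% of scheduled doses between visits must be immediately reported" to the Medical Monitor.

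**The concern.** A compliance ratio should fall when scheduled doses are not taken. Here the denominator ends at the last dose taken, so days without tablets before the visit are not counted as missed. An equal number of missed doses scattered through the interval is counted in full. Two subjects with the same intake can fall into opposite classes depending only on where the gap lies.

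What is at stake is the by-visit compliance table. In a 104-week outpatient study, stopping tablets some days before a visit that is still attended is a plausible form of non-adherence, and the by-visit rate cannot see it. For such gaps the table can err only towards better adherence. A subject reported to the Medical Monitor under Protocol 9.2 may appear as compliant for the same interval in the study report.

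**Working it through.** The plan states no numerical result to reproduce, so the check applies its formula directly.

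**Inputs.** Formula and limits: SAP 2.2.2.3. Comparison base (scheduled doses between visits) and limits: Protocol 9.2. A 28-day interval: the 4-week supply in Protocol 10.4 and the 4-week visit spacing from Week 8. Assumptions: daily intake up to the stop, all unused tablets returned, the next scheduled visit attended, and dosing resumed afterwards.

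**Formulas.** Let *t* be tablets per day, *L* the scheduled days in the interval, and *d* the day of the last dose, with the first dose on day 1.

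- SAP rate = 100 × (*t* × *d*) / (*t* × (*d* − 1 + 1)) = 100% for every *d*.
- Scheduled-dose rate = 100 × (*t* × *d*) / (*t* × *L*) = 100 × *d* / *L*.

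The daily tablet number cancels, so the result is the same at one or two tablets a day. The limits agree, since missing more than 25% means taking less than 75%. Only the denominators differ.

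**28-day interval.**

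| Last dose on day | SAP rate | Scheduled-dose rate | Same class? |
|---|---|---|---|
| 1 | 1/1 = 100% | 1/28 = 3.6% | No |
| 7 | 7/7 = 100% | 7/28 = 25.0% | No |
| 14 | 14/14 = 100% | 14/28 = 50.0% | No |
| 20 | 20/20 = 100% | 20/28 = 71.4% | No |
| 21 | 21/21 = 100% | 21/28 = 75.0% | Yes (compliant) |
| 28 | 28/28 = 100% | 28/28 = 100% | Yes (compliant) |

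**Position of the gap.** If the same 14 doses are missed at scattered times, with the first dose on day 1 and the last on day 28, the SAP rate is 14/28 = 50%, which is non-compliant.

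**Permanent discontinuation.** The schedule of assessments places the discontinuation visit within 48 hours of the last dose. With the last dose on day 14, the scheduled-dose rate lies between 14/14 = 100% and 14/16 = 87.5%. This is compliant on both bases.

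**52-week and overall rates.** Take 728 days with one half-missed 28-day interval followed by resumption.

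- One span from first to last dose: (728 − 14)/728 = 714/728 = 98.1%. The gap counts but is diluted. Thirteen such intervals give (728 − 182)/728 = 546/728 = 75.0%, still compliant.
- Visit spans summed: 714/714 = 100%. The gap is lost.

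**The case against.** The case against has five parts.

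*Last dose date is not defined in SAP 2.2.2.3, and the eCRF completion rules are not available.* This is correct. Reading it as the last dose taken rests on the kit dosing dates in that section and in Protocol 10.7, and on the parallel wording of SAP 2.2.2.4. No section supports extending it to the visit date. If that was the intention, the remedy is still to write it down.

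*Protocol 9.2 is a reporting trigger, not an analysis definition.* This stands. Protocol Section 14 specifies no compliance analysis, so the SAP breaks no protocol analysis rule. It does take over the same limits and change the base without saying so.

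*A reader might infer that no gap before a visit can ever give non-compliance.* The documents do not support that. A single-span 52-week or overall rate does count a gap followed by resumption. The 100% also depends on full return of unused tablets. A one-tablet carton holds 4 × 9 = 36 tablets (Protocol 10.2.1). If the subject stops after day 14 and returns 18 of the 22 unused tablets, tablets taken become 36 − 18 = 18, and 18/14 = 128.6% is non-compliant.

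*A reader might also infer that everyone who stops mid-interval is misclassified.* Those who stop for good are not, if the discontinuation visit takes place on time.

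*A reader might infer that the effectiveness and safety results are made to look as if they came from better-treated subjects.* This goes too far. The only analysis population is Safety, nobody is excluded for non-compliance, and there is no inferential test. Average daily dose (SAP 2.1.10) may also reflect interior gaps if untaken days carry zero dose. Disposition tables and the Kaplan-Meier plot show discontinuation.

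What remains is the by-visit rate for subjects who interrupt, attend and resume. No other part of the SAP corrects it.

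**Conclusion.** The point holds for the by-visit rate. Under the assumptions stated with the calculation, a subject who temporarily stops before an attended visit is rated 100% whatever the length of the gap. The number in the class below 75% is therefore too low by the number of such intervals with a gap of eight days or more out of 28. The documents do not say how often this happens, so the effect on the tables cannot be given. Whether the longer-period rates share the fault depends on how they are built. SAP 2.2.2.3 says only that, when kit data are incomplete for some visits, the other visits are used. The consequence is a descriptive table that is too favourable and may not match the reports under Protocol 9.2. It is worth correcting because the correction is cheap, but it does not threaten the study's conclusions.

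**What to change.** In SAP 2.2.2.3, define the by-visit number of tablets that should have been taken as tablets per day times the days from the first scheduled dose after dispensing to the next accountability or return visit. Where no kit is dispensed at Week 2 or Week 6, which happens unless the dose changes, the denominator should cover the whole span of the kit. End the denominator at the recorded last dose date only in the interval in which the subject permanently discontinues. Because dosing is normally in the evening, add one line on how the visit-day dose is counted. For the 52-week and overall rates, sum these same denominators, with the matching numerators, over visits with complete kit data. The exposure-day version may stay as a supplementary measure.

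With this rule, a temporary stop after day 14 of 28 gives 14/28 = 50% and is classed non-compliant.

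I would not add an exclusion for interruptions directed by the investigator. Protocol 10.7 lists no interruption dates, and Appendix C records an interruption only as an action taken for an adverse event. Such days will count as missed, and a footnote should say so.

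The cost is one definition, some reprogramming from visit dates and kit records, and slightly less favourable compliance figures. The schizophrenia report was completed on final database lock 1, so its compliance tables need a rerun or a footnote. The full report after lock 2 can carry the corrected definition for all subjects.
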